5. ETHICS

This clinical study will be conducted in accordance with the principles of the Declaration of Helsinki, and in compliance with the International Conference on Harmonization (ICH) E6 Good Clinical Practice (GCP) as described in 21 CFR §312 Consolidated Guideline and other regulations as applicable. The Investigator and all clinical study staff will conduct the clinical study in compliance with the protocol. The Investigator will ensure that all personnel involved in the conduct of the study are qualified to perform their assigned responsibilities through relevant education, training, and experience. Before initiating the clinical study, this protocol, the informed consent form any other written information given to patients, and any advertisements planned for patient recruitment must be approved by and by the Institutional Review Board (IRB) of the study sites. The Investigator must provide documentation of the IRB approval to Dompé. The approval must be dated and must identify the applicable protocol, amendments (if any), informed consent form, all applicable recruiting materials and written information for patient. The IRB must be provided with a copy of the Investigator's Brochure, any periodic safety updates, and all other information as required by local regulation and/or the IRB. At the end of the study, the Investigator will notify the IRB about the study completion. The IRB also will be notified if the study is terminated prematurely. Finally, the Investigator will report to the IRB on the progress of the study at intervals stipulated by the IRB.

Voluntary informed consent will be obtained from every patient (and/or impartial witness, as applicable) prior to the initiation of any study-related procedures. The Investigator must have a defined process for obtaining consent. Specifically, the Investigator, or designee, will explain the clinical study to each potential patient and the patient must indicate voluntary consent by signing and dating the approved informed consent form. The patient must be provided an opportunity to ask questions to the Investigator, and if required by local regulation, to other qualified personnel. The Investigator must provide the patient with a copy of the consent form written in a language the patient can understand. The consent document must meet all applicable local laws and will provide patients with information regarding the purpose, procedures, requirements, and restrictions of the study, along with any known risks and potential benefits associated with the investigational product and the established provisions for maintaining confidentiality of personal information. Patients will be told about the voluntary nature of participation in the study and will be provided with contact information for the appropriate individuals should questions or concerns arise during the study. The patient also will be told that their records may be accessed by appropriate

authorities and Dompé-designated personnel. The Investigator must keep the original, signed copy of the consent and must provide a duplicate copy to each patient.

6. PROTOCOL AMENDMENTS

Modification of the protocol is prohibited without prior written agreement in the form of a protocol amendment. All amendments will be created by Dompé and must be approved by the national competent authorities and/or IRB prior to implementation except when required to mitigate immediate safety risks or when the changes involve only logistical or administrative revisions.

Amendments may necessitate that the informed consent and other study-related material be revised. If the consent form is revised, all patients currently enrolled in the study may be required by the IRB to sign the approved, revised informed consent form.

7. PATIENT POPULATION

Adult patients with chronic primary open angle glaucoma with documented evidence of clinical progression prior to enrollment despite maximal current therapy (i.e. IOP reduction), or with stabilized IOP but diminished vision (central or peripheral). 60 patients (2:1 randomization active vs placebo) will be enrolled in the study.

To participate in the study, patients must be 18 or older with primary open angle glaucoma with documented evidence of clinical progression (i.e. progressive optic).

Patients must fulfill all of the study inclusion and none of the exclusion criteria listed in the protocol synopsis in Section 1 and below. If a patient can't read the informed consent due to poor vision, he/she can received the information verbally by another person but this procedure has to be documented, signed and dated by the independent person reading the document.

7.1 INCLUSION CRITERIA

1- Patients 18 years of age or older. Participant must understand and sign the informed consent. If the participant's vision is impaired to the point where he/she cannot read the informed consent document, the document will be read to the participant in its entirety.

2- Participant's clinical diagnosis must be consistent with glaucoma characterized by the following features: a) clinical evidence of progressive RGC dysfunction and degeneration using visual field and/or a structural modality. There must be at least 3 reliable visual fields within 14 months prior to entering into the study; b) residual visual field preservation in at least 1 quadrant.

3- Participant must be medically able to undergo the testing required in the flowsheet of exam procedures.

4- Females of childbearing potential must agree to use an effective form of birth control.

7.2 EXCLUSION CRITERIA

1- Participant has another optic nerve or retinal degenerative disease or co-morbidity causing significant vision loss, irrespective of whether it is currently treated or untreated, that could limit the possibility of visual recovery.

2- Participant is blind in one eye.

3- Participant has a requirement of acyclovir and/or related products during study duration.

4- Participant has evidence of corneal opacification or lack of optical clarity.

5- Participant has undergone lens removal in the last 3 months, with or without intra-ocular lens implantation, or has undergone intra-ocular lens replacement within 3 months, or has undergone any other ocular surgery within 9 months prior to initiation of study drug.

6- Participant is receiving systemic steroids or other immunosuppressive medications.

7- Participant is currently participating in or has within the last 3 months participated in any other clinical trial of a non-clinically approved drug by ocular or systemic administration.

8- Participant has uveitis or other ocular inflammatory disease.

9- Participant has diabetic macular edema.

10- Participant has a history of ocular herpes zoster.

11- Participant is on chemotherapy.

12- Participant has a history of malignancy, not counting basal cell carcinomas, UNLESS it was treated successfully 2 years prior to inclusion in the trial.

13- Known hypersensitivity to one of the components of the study or procedural medications.

14- History of drug, medication or alcohol abuse or addiction.

15- Females of childbearing potential (those who are not surgically sterilized or post-menopausal for at least 1 year) are excluded from participation in the study if they meet any one of the following conditions:

- a. are currently pregnant or,
- b. have a positive result on the urine pregnancy test at the Screening/Baseline Visit or,
- c. intend to become pregnant during the study treatment period or,
- d. are breast-feeding or,
- e. not willing to use highly effective birth control measures, such as: Hormonal contraceptives – oral, implanted, transdermal, or injected and/or mechanical barrier methods – spermicide in conjunction with a barrier such as a condom or diaphragm or IUD during the entire course of and 30 days after the study treatment periods.

Important Notes:

All females of childbearing potential must consent to a urine pregnancy test upon entering and exiting the study treatment period. Females of childbearing potential must agree to immediately inform the Investigator if they become pregnant during the study.

For non-sexually active females, abstinence may be regarded as an adequate method of birth control; however, if the patient becomes heterosexually active during the study treatment period, she must agree to use adequate birth control methods as defined above for the remainder of the study treatment period.

Pregnancy should be avoided in patients or partners during the first month after completing the treatment with the Investigational Product.

8. TREATMENTS ADMINISTERED

Upon entry into the study, patients will be assigned randomization numbers in the appropriate numerical sequence by the Investigator. Each eligible subject will be assigned to a randomization number according to the sequence of study entry, from 01 to 60.

8.1. 8 WEEK RANDOMIZED CONTROLLED TREATMENT PERIOD

The 8 week (2 months) double-masked, randomized, controlled treatment period, (hereafter, also referred to as the controlled treatment period) will be followed by a 24 week (6 months) follow-up period. Enrolled patients will be randomized at baseline in a 2:1 ratio to the active treatment arm (rhNGF 180 µg/ml, one drop TID) or the vehicle control arm (vehicle, one drop TID in the affected eye(s)) as shown below in the Table 8.1-1.

Table 8.1-1. – Treatment Arms

| Treatment arm | Treatments |
|---------------|---|
| 1. Active | 180 µg/ml rhNGF, one drop TID (in both eyes if bilateral disease) |
| 2. Control | Vehicle control, one drop TID (in both eyes if bilateral disease) |

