|-------------------------------------|---|--|
| Study Population: | Adult patients with chronic primary open angle glaucoma with documented evidence of clinical progression prior to enrollment despite maximal current therapy (i.e. IOP reduction), or with stabilized IOP but diminished vision (central or peripheral). | |
| Total duration of the study: | 
Maximum total study duration 32 weeks (8 months).
 
There will be three periods in this study:
 
1) a 8 week phase Ib double-masked, randomized, controlled treatment period.
 
and
 
2) a 4 week masked follow-up period.
 
and
 
3) a 20 week unmasked follow-up period.
 | |
| Treatments: | Test product: rhNGF 180 µg/ml eye drops solution | |
| | Administration: | Topical, ocular |
| | Duration of controlled treatment period: | 8 weeks |
| | Quantity/Dosage: | Eligible patients will self-administer 1 drop of rhNGF 180 µg/ml three times a day (TID) for 8 weeks in both eyes. |
| | Control: Vehicle | |
| | Administration: | Topical, ocular |
| | Duration of controlled treatment period: | 8 weeks |
| | Quantity/Dosage: | Eligible patients will self-administer 1 drop of vehicle three times a day (TID) for 8 weeks in both eyes. |

| | |
|---------------------------|--|
| Subject Selection: | Inclusion Criteria: |
| | 1. Patients 18 years of age or older. Participant must understand and sign the informed consent. If the participant's vision is impaired to the point where he/she cannot read the informed consent document, the document will be read to the participant in its entirety. |
| | 2. Participant's clinical diagnosis must be consistent with glaucoma characterized by the following features: a) clinical evidence of progressive RGC dysfunction and degeneration using visual field and/or a structural modality. There must be at least 3 reliable visual fields within 14 months prior to entering into the study. b) residual visual field preservation in at least 1 quadrant. |
| | 3. Participant must be medically able to undergo the testing and study procedures required in the flowsheet of exam procedures. |
| | 4. Females of childbearing potential must agree to use an effective form of birth control. |

| Exclusion Criteria: |
|--|
| 1. Participant has another optic nerve or retinal degenerative disease or co-morbidity causing significant vision loss, irrespective of whether it is currently treated or untreated, that could limit the possibility of visual recovery. |

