**Table 9.1.2-1 - Kit Assignments**

| Weekly visit | # of kits |
|---|------------------|
| Day 0 - Randomization / Therapy initiation Visit | 1 kit |
| Week 4 Visit | 1 kit |

Study medications that will be dispensed to the patient during the study visits will be distributed in refrigerated bags. In addition to the study medication to be administered in the clinic on the day of the study visit, patients will also be instructed to bring back to the clinic at each study visit all the used and unused vials by placing them in the refrigerated bag that was given at the Day 0 visit (so that it can be used for dispensing the next kit, if applicable).

Each 4 week kit will be composed of 1 box containing a total of 90 single-use vials of the randomized / assigned medication for daily treatment during 4 weeks and 1 box containing the same number of adaptors and prefilled 0.3 ml WFI syringe.

All patients will be dosed one drop (35 µl) three times a day (TID) in each eye during the 8 weeks, randomized, double-masked, controlled treatment period.

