9.1.3. Usage

All study drugs used in this study are for topical ocular usage only. Dispensing of the study medications to the patients will be performed as described in Section 9.1.2 and table 9.1.2-1.

All patients will be dosed one drop (35 µl) TID in each eye every morning, afternoon and evening as shown in the **Table 9.1.3-1**. The timing of instillation should be adjusted if a patient's awakening and/or bedtime differs.

Patients will begin treatment in the clinic at the Day 0 visit, where he/she will be shown how to resuspend the lyophilized molecule and instill the eyedrops in the eyes. For this purpose, a training manual with detailed instructions on how to reconstitute the eye drops will be provided to the investigators (see Appendix A). Patients will then be instructed to self-administer the study medication one drop three times a day through 8 Weeks of the controlled treatment period. During the 8 week controlled treatment period patients will be instructed to return to the clinic on the monthly visits with the used kits and empty (used) vials as well as

with the daily kit of study medication and vials to be used on the day of the study visit in the refrigerated bag that will be given when the study medication is dispensed.

Table 9.1.3-1. – Dosing Schedule

| TREATMENT | TREATMENT DOSING SCHEDULE |
|-----------------------------------|--------------------------------|
| rhNGF 180 µg/ml or Vehicle | Morning (approximately 8 AM) |
| | Afternoon (approximately 2 PM) |
| | Evening (approximately 8 PM) |

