**9.1.5. Storage**

Investigational product must be stored in a secure area at the investigational site as per the labeling instructions. A temperature probe and data logger will accompany the drug on shipment. It is essential that the Investigational sites verify the temperature range reached during shipment, so that potential stability concerns during shipment can be discovered and appropriate action taken. The box of the investigational product containing the lyophilized preparation must be stored at 2-8°C at the Investigational sites (preferably at the pharmacy of the hospital), whereas the box containing the prefilled syringes and adaptors may be kept at room temperature. Eligible patients will receive the first 4-week kit of study medications in a refrigerated bag containing the investigational product. The vehicle control will be also dispensed in a refrigerated bag. The patient will be instructed to store the study medication (the box of the investigational product containing the lyophilized preparation) at home in the refrigerator at 2-8 °C for the entire 4 weeks until next visit. The box containing the prefilled syringes and adaptors may be kept at room temperature. When the patients will start to use the study medications at home each day they will remove from the refrigerator only the vials to be used over the course of the day. Patients will use one vial to instill one drop in both eyes three times per day.

A daily temperature log will be maintained at the site for documenting appropriate storage conditions and will be made available for the study monitor to inspect. Any deviations from the recommended storage conditions should be immediately reported to Dompé and the use of the drug suspended until authorization for its continued use has been given by Dompé.

Investigational products will be supplied as a lyophilized preparation in glass vials together with a prefilled 0.3 ml sterile WFI syringes and adaptors. The vials will be labeled with the appropriate clinical study labeling. The vehicle of rhNGF will be supplied in glass vials identical to those containing rhNGF with a prefilled 0.3 ml WFI syringes and adaptors. The vials containing the vehicle will be labeled with the appropriate clinical study labeling. Investigational product will be kept in an identical box to ensure double-masking.

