12.8. OVERDOSE

Cases of overdose (accidental or intentional) which result in serious adverse reactions are to be handled following emergency procedures, and reported within 24 hours from the Investigator's knowledge of its occurrence. This includes reports related to drug intake through different routes (e.g. ingestion), or drug intake with suicidal intentions and consequent drug overdose.

Since in the preclinical toxicology studies in animals and in the multiple ascending dose study performed in healthy volunteers none of the doses has caused an overdose, as documented by adverse reaction, for the purpose of this study it has been defined that the administration of more than 3 times the total daily dose on any given treatment day will be reported as an overdose.

Overdose shall be reported, even if not associated with adverse reactions, within 24 hours, in a SAE form, to CRO/Dompé Drug Safety contacts reported at Paragraph 12.4.1 and to Dompé Medical Expert, who should be contacted to discuss corrective treatment, if necessary.

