6.1 Analysis Sets

Evaluability for all patients and visits will be determined during a Blind Data Review Meeting, which will take place before unmasking the study for the main objective analysis (i.e. comprising data up to Week 12 Visit).

The Total Set (TOT) will include all patients that have signed informed consent.

The Intent-to-treat Set (ITT) will include all randomized patients and will be used for all exploratory efficacy analyses. All analyses based on the ITT will be summarized by the treatment randomized.

The Safety Set (SAF) will include all randomized patients who receive at least one dose of study medication. This safety population will be used in the analysis of all safety endpoints.

A subset of all patients in the SAF, who entered the Follow-Up Period (SAF-F), will be used in addition to present event-type analyses of the Follow-Up Period. A patient will therefore be considered as entering the Follow-Up Period, if he/she did not terminated the study at or before the Week 8 visit.

All analyses based on the SAF and SAF-F will be summarized by the treatment received.

For the study, both eyes are under investigation. For each patient, a Primary (Study) Eye and a corresponding Secondary Eye will be defined during a Blind Data Review Meeting (BDRM) to enable a patient based presentation of statistical analyses.

For each patient, an eye will be considered as Primary Eye, if

- the eye was treated and
- the investigator considered this eye as qualifying eye.

If both eyes are considered as qualifying eye, the right eye will be chosen.

The other eye will then be considered as Secondary Eye, if the eye was treated. If the other eye was not treated with study medication, no Secondary Eye will be assigned for this patient.

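### The protocol gives two dosing rules, both eyes for every patient or both eyes only if disease is bilateral; they part for patients with unilateral disease and leave the overdose trigger unclear for them

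*Protocol*

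**What the plan says.** Two rules stand in the current text.

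**Unconditional.** The synopsis has "Eligible patients will self-administer 1 drop of rhNGF 180 µg/ml three times a day (TID) for 8 weeks in both eyes", with the same instruction for vehicle. Protocol 9.1.2 has "All patients will be dosed one drop (35 µl) three times a day (TID) in each eye during the 8 weeks", and 9.1.3 has "All patients will be dosed one drop (35 µl) TID in each eye every morning, afternoon and evening". Section 9.1.5 (Storage) repeats it: "Patients will use one vial to instill one drop in both eyes three times per day". The arm table in 10.1.1 lists both eyes for both arms without a condition. SAP 3.2 and 7.2.5 carry the same rule.

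**Conditional.** Table 8.1-1 gives each arm "one drop TID (in both eyes if bilateral disease". The text of 8.1 above the table confines drops to the affected eye or eyes, but attaches those words to the vehicle arm only. For the active arm it names no eye.

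Three other provisions depend on which rule is followed:

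- Protocol 12.8 says that "administration of more than 3 times the total daily dose on any given treatment day will be reported as an overdose". It never gives the total daily dose as a number. Such an overdose goes to drug safety within 24 hours on an SAE form, even without an adverse reaction.
- SAP 7.2.7 counts unexpected severe progression of optic neuropathy (USPON), a primary safety outcome, in treated eyes only.
- SAP 6.1 provides for an untreated fellow eye: "If the other eye was not treated with study medication, no Secondary Eye will be assigned for this patient".

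**The concern.** The primary objective is safety and tolerability, so which eyes receive drug is a basic instruction. A site working from Section 8, which is titled for the treatments administered, and a site working from Section 9 could treat the same patient differently.

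The patient for whom the rules part is foreseen. The synopsis admits patients with a qualifying eye, and SAP 7.2.3 has categories for symptoms in the right eye only, the left eye only, or both. Excluding patients who are blind in one eye does not exclude unilateral glaucoma.

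For that patient three things are at stake: whether a fellow eye without disease is exposed to study drug, how many drops in a day oblige the site to file an overdose report, and whether one eye or two are at risk for USPON.

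**Working it through.** **Inputs**

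- Drop volume 35 µl, concentration 180 µg/ml, 6.30 µg per drop (Protocol 9.1).
- Three drops per treated eye per day (all sections agree).
- 56 expected treatment days (SAP 7.2.5).
- Overdose multiple of 3 (Protocol 12.8).
- 60 patients, 40:20 (synopsis).
- Share with unilateral disease: not in the documents. Assumed at 0%, 10%, 25% and 50% to show the range.

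**Step 1: the plan's own figure.** 0.035 ml × 180 µg/ml = 6.30 µg per drop. This agrees with Protocol 9.1.

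**Step 2: dose and overdose trigger for one patient.** Daily dose = 6.30 × 3 × treated eyes. Eight-week dose = daily dose × 56. Trigger = more than 3 × daily dose.

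| | One eye treated | Both eyes treated |
|---|---|---|
| Drops per day | 3 | 6 |
| Daily dose | 6.30 × 3 = 18.9 µg | 6.30 × 6 = 37.8 µg |
| Eight-week dose | 18.9 × 56 = 1058.4 µg | 37.8 × 56 = 2116.8 µg |
| Overdose reported above | 9 drops, 56.7 µg | 18 drops, 113.4 µg |

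The ratio is 2 in every row. A patient with unilateral disease who takes 12 drops in a day receives 12 × 6.30 = 75.6 µg. That is reportable if the daily dose is 18.9 µg and not reportable if it is 37.8 µg. The same holds for any count from 10 to 18 drops.

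**Step 3: how many patients.** Patients affected = 60 × unilateral share.

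| Assumed share | Patients for whom the rules differ | Patients with a Secondary Eye if the condition is applied |
|---|---|---|
| 0% | 0 | 60 (40:20) |
| 10% | 6 | 54 (36:18) |
| 25% | 15 | 45 (30:15) |
| 50% | 30 | 30 (20:10) |

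The splits by arm assume the same share in each arm. Under the unconditional rule the last column is 60 throughout.

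**Step 4: does another section settle it?** No. Protocol 8.1.1 equates one dose with one drop and names no eye. The SAP's treatment labels (Table 3) give one drop TID and no number of eyes. If both eyes were always dosed, the condition in Table 8.1-1 would have no function. If the condition governs, the statements in 9.1.2 and 9.1.3 about all patients are wrong.

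**Step 5: do planned outputs change?** Extent of exposure (Protocol 11.5.3, SAP 7.2.5) is in days. Compliance counts vials, and under 9.1.5 one vial serves both eyes. Neither depends on the number of eyes dosed. The number of patients with one treated eye is already planned: SAP 7.2.3 defines Secondary Eye with a category None, SAP 10.4.2.1 summarises it in Table 14.1-4.1, and SAP 8.1 reports categorical variables by treatment group.

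**The case against.** The strongest case on the other side is that the unconditional rule appears in seven places and the SAP works under either rule. Primary and Secondary Eyes are assigned at the blind data review from the eyes actually treated. Untreated eyes are listed and not analysed (SAP 8.1), and USPON is confined to treated eyes. All of that stands. It limits the point to the instruction in the protocol, but does not remove the contradiction there.

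Four stronger readings are tempting, and the documents do not support them.

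- *The exposure tables would be wrong.* They report days, so they would not change. Only the micrograms received change, and no planned table reports those.
- *The Secondary Eye set is ill defined.* Its size depends on the rule followed, but its definition holds under both.
- *The arms are dosed differently, or the comparison is biased.* The 8.1 text limits only the vehicle arm to affected eyes, but Table 8.1-1 applies the same condition to both arms. The study has one centre, is double-masked and uses vials of identical appearance. Nothing suggests that the site would apply different eye rules by arm.
- *Two overdose thresholds are themselves an error.* A threshold set as a multiple of the daily dose may properly differ between patients with one and two treated eyes. The defect is narrower: for a patient with unilateral disease the prescribed daily dose is not settled, so neither is its multiple.

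It is also fair to say that Table 8.1-1 does not state what happens in unilateral disease. One-eye dosing is an inference.

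**Conclusion.** The inconsistency is real and the text is wrong as written. Table 8.1-1 and the 8.1 text cannot both stand with the synopsis, Protocol 9.1.2, 9.1.3, 9.1.5 and 10.1.1, and SAP 3.2 and 7.2.5.

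Its reach is limited to patients with unilateral disease. It is nil if every patient has bilateral disease, and otherwise grows with a share that the documents do not give. For each such patient the daily dose and the overdose trigger differ by a factor of 2, and fellow-eye exposure and the number of eyes at risk for USPON are open. The factor of 2 rests on reading Table 8.1-1 as one-eye dosing in unilateral disease.

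The fault lies in the treatment instruction and in a mandatory safety report, not in the SAP's analysis rules. It should be corrected because it bears on safety and costs little. The documents do not show which rule was intended, and this review does not choose one.

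**What to change.** Issue a protocol clarification, an instrument this study has already used (SAP 3.6, for the visual field algorithm), that does two things:

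1. Reconcile Section 8.1 and Table 8.1-1 with the synopsis, Protocol 9.1.2, 9.1.3, 9.1.5 and 10.1.1, and SAP 3.2 and 7.2.5, so that one rule stands for both arms. The sponsor decides which.
2. In Protocol 12.8, state the total daily dose from which the overdose threshold is computed, and whether it is per treated eye or per patient.

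The cost is one clarification letter and matching wording in the SAP sections named. No table, analysis set or program changes, since the count of patients with Secondary Eye None in Table 14.1-4.1 will show by arm how many had one treated eye.
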